7.2.3 Psychological Distress

Mild anxiety and depressed mood are occasionally reported one to three days after MDMA administration [13, 15, and see the IB]. Psychological distress from MDMA could arise at any time from the first indications of drug effects until the last effects have dissipated (approximately three to five hours after drug administration), or even later. Any anxiety or distress occurring during the session may last for as little as five minutes or for as long as five hours or more. In addition, psychological distress could arise following an MDMA-assisted session as a result of participants having difficulty integrating their experience after the MDMA effect has subsided. In previous Phase 1 and Phase 2 studies, these symptoms have been self-limiting, and have responded well to reassurance from the therapists, with occasional use of benzodiazepines for anxiety. In

this study, participants will have the intention of confronting and working through traumatic experiences. Hence signs of psychological distress, panic or other unpleasant psychological reactions are to be expected and may be considered an element of the psychotherapeutic process.

Proper preparation and follow-up support will reduce the difficulties participants might have with acute or sub-acute reactions. The potential for destabilizing psychological distress will be minimized by:

- Excluding people who might be more vulnerable to it (such as people diagnosed with bipolar affective disorder-1 or with psychotic disorders)
- Preparatory non-drug psychotherapy sessions before the Experimental Session.
- Creating an atmosphere of trust during the Experimental Session
- Close monitoring
- Daily contact with participants for the period of a week after the Experimental Session
- Providing non-drug psychotherapy Integrative Sessions
- Participants will remain at the study site for the night of each Experimental
 Session to further reduce psychological distress. Qualified personnel will be
 available during the overnight stay to respond to the needs of the participants.
 Attendants will be instructed to contact the therapists upon request or at the
 appearance of signs of a potential serious adverse event.

During the Preparatory Sessions, participants will be made aware of the fact that difficult emotions, including grief, rage and fear or panic, may arise during Experimental Sessions. Every effort will be made to help participants resolve difficult symptoms and to arrive at a more comfortable and relaxed state by the conclusion of the Experimental Session, including empathic listening on the part of the therapists and performance of diaphragmatic breathing or other stress inoculation techniques by participants.

At the end of the Experimental Session, which lasts six to eight hours, if the PTSD+ participant or CSO participant is still severely agitated or experiencing any other severe psychological distress, the following measures will be taken:

- If the PTSD+ participant or CSO participant is anxious, agitated, in danger of any self-harm or is suicidal at the end of the Experimental Session, the therapists will remain with them for at least two more hours. During this time, the therapists will employ affect management techniques, will talk with the participant to help them gain cognitive perspective of their experiences, and will help them implement the self-soothing and stress inoculation techniques presented during the Preparatory Session. If this situation should occur during an Integrative Session, at least one of the therapists will be available to stay with the person for at least two additional hours.
- If a PTSD+ participant or CSO participant remains severely anxious, agitated or in danger of self-harm or suicide, or is otherwise psychologically unstable at the end of this two-hour stabilization period, the Clinical Investigator will decide between the following options:

Page 64 of 89

- 1. A psychiatric nurse, therapeutic assistant, physician, or therapist will stay with the PTSD+ participant or CSO participant until the time of their appointment with the therapists the next day. The therapists will then meet with the participant daily until the period of destabilization has passed.
- 2. If a PTSD+ participant or CSO participant experiences severe, persisting emotional distress, such as panic attacks, severe generalized anxiety, or insomnia following an MDMA-assisted session, the study physician may prescribe a rescue medication such as a benzodiazepine, zolpidem, or other anxiolytic or sedative according to the physician's clinical judgment. This medication will be captured on the concomitant medications CRF page. The physician should not prescribe an SSRI, SNRI or MAOI in this context unless it has been determined that the participant will be withdrawn from the study. Residual symptoms will be addressed during the frequent follow-up psychotherapy visits with the therapists.
- 3. Hospitalization for stabilization. If a PTSD+ participant or CSO participant should become psychotic arrangements will be made to stabilize them and transfer them to the ED if necessary.

PTSD+ participants or CSO participants hospitalized after a severe panic reaction will be suspended from the protocol until after recovery or stabilization, at which time the Clinical Investigators will carefully evaluate their emotional status.

For those PTSD+ participants or CSO participants engaged in an ongoing therapeutic relationship with a psychotherapist or psychiatrist, the outside therapists will be involved in the management of any psychiatric complications. For those PTSD+ participant or CSO participants engaged in an ongoing psychotherapeutic relationship with the Clinical Investigators, the management of any psychiatric complications will be undertaken by them in their capacity as therapists.

7.2.4 Body Temperature

MDMA administered in a controlled setting produces only a slight increase in body temperature [15] and ambient temperature does not enhance or attenuate this slight elevation in humans.

If temperature rises more than 1°C, attempts will be made to lower it by removing blankets and layers of clothing, decreasing the ambient temperature and, if necessary, directing a fan toward the participant. If at any time the temperature rises more than 1.5°C above Baseline despite these efforts, the study physician will be consulted for further evaluation and treatment

7.2.5 Reproductive and Developmental Risks

Risks posed by MDMA to pregnant persons are not known. One of two studies of Ecstasy users suggests that use of Ecstasy and other drugs during pregnancy may be associated with some abnormalities at birth while the other failed to find this association [189, 190], and a third reported some developmental delays in mothers reporting use of and other drugs during pregnancy [191] as discussed in the IB.

Pregnant and lactating persons will be excluded from participation in the study, and participants who are able to become pregnant must have a negative pregnancy screen before undergoing each Experimental Session and must agree to use birth control for the treatment portion of the study.

7.2.6 Potential Neurotoxicity Associated with Ecstasy Use

Some researchers believe that MDMA is neurotoxic in humans even at doses used in clinical trials [192]. However, they are basing their case on studies that employed inappropriately high doses of MDMA utilized in animal studies, and on human studies comparing the effects of repeated use of MDMA, often along with other drugs. Meanwhile, another recently published meta-analysis has taken careful steps to overcome methodological limitations in previous work, and found only modest evidence of neurotoxicity [193]. We have carefully considered the risks of such neurotoxicity and conclude that they are minimal in the proposed study. This conclusion is supported by empirical and toxicokinetic evidence and is consistent with the lack of toxicity reported in previous clinical MDMA studies. More information on the potential neurotoxicity of MDMA can be found in the IB.

7.2.7 Risk Mitigation

Careful review of medical screening data will be utilized to exclude potential participants with pre-existing exclusionary medical conditions from the study. Study procedures have been developed to mitigate the risks of receiving MDMA described in detail in the IB. Ambient temperature will be kept at a comfortable level during Experimental Sessions. Participants will not be allowed to drink more than 3L of fluids over the course of the Experimental Session, and fluid intake will be spread out appropriately during the session. Fluids administered will include electrolytes. If a participant exhibits any signs of toxicity or clinically significant dilutional hyponatremia despite these precautions after an Experimental Session, they will not be given another Experimental Session unless it is approved by the Clinical Investigator, study physician, and the Medical Monitor.

7.3 Abuse Liability

Findings in humans and animals suggests that MDMA possesses moderate abuse potential that is higher than that reported for "classic hallucinogens" like psilocybin, but lower than that reported for psychostimulants such as cocaine or methamphetamine. More information on abuse liability is provided in the IB.

Whether MDMA-assisted psychotherapy will cause some PTSD patients to develop an MDMA use disorder is an open question that the sponsor is addressing on an ongoing basis. Based on Long-term Follow-up data from two sponsor-supported studies (N=32), only one participant took Ecstasy after completing the study and failed to reproduce the experience from the study, and a number of participants volunteered that they would never seek out Ecstasy outside a legal, controlled, therapeutic setting. In addition, negative results from MDMA-specific drug testing data obtained from the Swiss study

MP-2 (N=12) supports that none of these participants took Ecstasy outside of the study during the Long-term Follow-up period.

Diversion is not an issue in this protocol because MDMA will only be administered a few times under the supervision of the Clinical Investigator and no take-home doses will be permitted. MDMA will be handled following all regulations pertaining to the handling and dispensing of controlled substances within research studies.

8.0 Adverse Events

8.1 Adverse Events

An adverse event (AE) is defined as any untoward or unfavorable medical occurrence in a clinical research study participant, including any abnormal sign (e.g. abnormal physical exam or laboratory finding), symptom, or disease, temporally associated with the participant's involvement in the research, whether or not considered related to participation in the research. This definition includes concurrent illnesses or injuries and exacerbation of pre-existing conditions.

An unexpected adverse event is one that is not listed in the current IB or an event that is by nature more specific or more severe than a listed event.

All AEs will be monitored by the therapists until resolution or, if the AE becomes chronic, a cause identified. If an AE is unresolved at the conclusion of the protocol, a clinical assessment will be made by the Clinical Investigator and/or Medical Monitor as to whether continued follow-up of the AE is warranted.

The severity of events reported on the "Adverse Events" CRF will be determined by the study physician as:

- Mild: no limitation in normal daily activity
- Moderate: some limitation in normal daily activity
- Severe: unable to perform normal daily activity

The relationship of the study treatment to an AE will be determined by the study physician based on the following definitions:

- 1. Not Related: the AE is not related if exposure to the investigational product has not occurred, or the occurrence of the AE is not reasonably related in time, or the AE is considered unlikely to be related to use of the investigational product, i.e. there are no facts (evidence) or arguments to suggest a causal relationship, or the AE is more likely related to the participant's pre-existing condition.
- 2. Possibly Related: the administration of the investigational product and AE are considered reasonably related in time and the AE could be explained by causes other than exposure to the investigational product.
- 3. Probably Related: exposure to the investigational product and AE are reasonably related in time and the investigational product is more likely than other causes to be responsible for the AE, or is the most likely cause of the AE.

8.2 Spontaneously Reported Reactions

Commonly expected spontaneously reported reactions are collected on a separate CRF page and will be categorized as mild, moderate, or severe. Common, expected reactions are defined as those most frequently reported in the literature and include: Anxiety, Diarrhea, Difficulty Concentrating, Dizziness, Drowsiness, Dry Mouth, Fatigue, Headache, Heavy Legs, Impaired Gait/Balance, Impaired Judgment, Increased Irritability, Insomnia, Jaw Clenching or Tight Jaw, Lack of Appetite, Low Mood, Muscle Tension, Nausea, Need More Sleep, Nystagmus, Parasthesias, Perspiration, Restlessness, Rumination (increased private worries), Sensitivity to Cold, Thirst, and Weakness. Spontaneously reported reactions will be collected during the Experimental Session and the seven days of telephone contact following the Integrative Session that occurs on the day after each Experimental Session. Each reported reaction will be actively followed during follow-up phone calls or visits until resolution. Any reported event that is not listed as a Spontaneously Reported Reaction will be collected as an Adverse Event following the plan in Section 8.5 Adverse Event Collection. Any common reaction lasting longer than seven days will be tracked as an adverse event in order to obtain a resolution date.

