7.2 Risks of Receiving MDMA

Spontaneously reported reactions and common adverse effects of MDMA are modest and have generally not been associated with serious discomfort by healthy volunteers in previous studies. Common reactions include lack of appetite, insomnia, dizziness, tight jaw or bruxism (tooth-grinding), difficulty concentrating, impaired gait or balance, dry mouth, ruminations, and thirst. Other slightly less common reactions include restlessness, parasthesias (odd somatic feelings, such as tingling, feeling hot or cold), impaired judgment, perspiration, drowsiness, and nystagmus (eye-wiggling). While anxiety, headache, fatigue, insomnia and lack of appetite were spontaneously reported by 40% to 80% of participants in both conditions in MAPS study MP-1 (N=23), tight jaw, nausea, impaired gait/balance, and sensitivity to cold were more often reported by participants in the MDMA than the placebo condition, and irritability was slightly more likely to be reported in the placebo condition. Additionally, participants in the MDMA condition were more likely to report muscle tension in various body parts and diarrhea.

These effects are transient and diminish as drug effects wane. Sub-acute effects that may either continue for the next 24 hours or appear later include insomnia, fatigue, needing more sleep, weakness, heavy legs, dry mouth, low mood or irritability. Sub-acute effects are reported less often than acute effects. More information on spontaneously reported reactions is described in the IB.

MDMA may produce mild alterations in sensory perception and altered perception of time [10, 109, 184]. Women may be more sensitive to these effects [15]. MDMA acutely affects attention, information processing, and memory. MDMA acutely impairs verbal memory and recall for object location without affecting recall of complex scene changes [185]. For this reason, participants will stay at the site overnight and will not be permitted to drive after Experimental Sessions.

MDMA may produce modest changes in immune functioning, lasting up to 48 hours. Because of their limited duration, these changes are not likely to have clinical significance beyond several days of possible increased risk of viral upper respiratory infection or similar illness.

Further information on the risks associated with MDMA, including information drawn from case reports and studies of users, can be found in the sponsor's Investigator Brochure.

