8.5 Adverse Event Collection

The study physician will be responsible for reviewing and confirming all AEs and SAEs collected during the study. The therapists will collect AEs during study/telemedicine visits after enrollment.

All SAEs will be collected for the duration of the protocol. All SAEs which occur during the course of the trial, whether considered to be associated with the study drug or not, have to be reported within 24 hours of the Clinical Investigator's awareness of their occurrence. All SAE reports should be faxed to the sponsor. A fax number will be provided to the site in separate site-specific instruction for SAE reporting. In addition to the fax, the study physician, Clinical Investigator, or designee should call the CRA during normal working hours and verbally inform the CRA of the SAE. During off business hours or if medical advice is needed immediately please call the sponsor Medical Monitor. An SAE reporting instruction with all contact numbers will be provided to the site prior to study start.

Medical Monitor:

Page 69 of 89

[name]. [name] [name] [name] [contact]

Study Monitor contact information will be provided in a separate contact list.

Adverse events that will be collected for the duration of the protocol are:

- All SAEs will be collected through participant termination
- All AEs and spontaneously reported reactions will be collected on the day of drug administration and for seven days after each Experimental Session
- Any spontaneously reported reactions that have not resolved to the PTSD+ participant's or CSO participant's Baseline level of severity after seven days will be collected on the Adverse Event Report page until resolution
- Events requiring medical attention will be collected from enrollment through the PTSD+ participant's or CSO participant's last follow-up
- Events related to planned treatments or physician visits for Baseline conditions collected in the Medical History will not be collected unless there is an exacerbation of the condition
- Any Adverse Event leading to withdrawal from the protocol will be collected throughout the study
- All AEs related to changes in psychiatric status will be collected throughout the study

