## 6. Safety Analyses

The primary measure of safety will be reports of adverse events. Adverse events are Treatment Emergent Adverse Events (TEAE) defined as those AE's that occurred after dosing and existing medical history diagnoses that worsened during the study. Verbatim terms on case report forms will be mapped to preferred terms and system organ classes using the MedDRA dictionary. For incidence reporting if a subject has more than one AE mapped to the same preferred term, that AE will be reported only once using the highest severity and closest relationship to study drug. Subject incidence of AEs will be displayed by group and by system organ class. AEs will also be summarized by severity. Subject incidence of SAEs will also be displayed. In addition to the listing of all AEs, a listing of SAEs and a listing of AEs leading to discontinuation of study drug will be included.

Summary tables of frequency listings of commonly reported AEs (Spontaneously Reported Reactions) mapped to preferred terms will be displayed during and after each experimental session by PTSD+ participants and CSO participants. Additional safety measures will be analyzed as follows:

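### A severe or medically treated listed reaction that resolves within seven days may never reach the AE tables, because protocol 8.2 and 8.5 do not say which rule governs and the SAP plans only frequencies for reactions

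*Protocol*

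**What the plan says.** Protocol 8.2 sets up a separate stream for expected reactions: "Commonly expected spontaneously reported reactions are collected on a separate CRF page and will be categorized as mild, moderate, or severe". The list mixes somatic and psychiatric terms; one stretch of it reads "Jaw Clenching or Tight Jaw, Lack of Appetite, Low Mood, Muscle Tension, Nausea, Need More Sleep", and Anxiety, Increased Irritability, Insomnia and Rumination are also on it. The section then divides the streams: "Any reported event that is not listed as a Spontaneously Reported Reaction will be collected as an Adverse Event". Its only route from the reaction page to the AE page is duration: "Any common reaction lasting longer than seven days will be tracked as an adverse event in order to obtain a resolution date".

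Protocol 8.5 repeats the seven-day transfer. It also has bullets for SAEs, events requiring medical attention, AEs leading to withdrawal, and psychiatric change: "All AEs related to changes in psychiatric status will be collected throughout" the study. None of these bullets exempts a listed term.

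Protocol 8.1 has the study physician grade severity, against stated definitions, for events reported on the AE CRF, and rate the relatedness of AEs. Section 8.2 gives no definitions for its three grades, names no rater and mentions no relatedness rating.

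For analysis, the SAP (6. Safety Analyses) states: "The primary measure of safety will be reports of adverse events". AEs are shown by system organ class and summarized by severity. For reactions it plans "Summary tables of frequency listings of commonly reported AEs (Spontaneously Reported Reactions) mapped to preferred terms", by experimental session and by PTSD+ and CSO participants. Protocol section 12.0 goes further and promises maximum severity and duration for reactions, overall and for the two participant groups.

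**The concern.** Psychological distress after dosing is a risk the protocol singles out in 7.2.3. That section foresees severe generalized anxiety or insomnia for which the study physician may prescribe a rescue medication. It says the medication goes on the concomitant medications page and does not say where the event goes. Section 7.2.1, by contrast, sends clinically significant treatment-emergent suicidality to AE collection explicitly.

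Anxiety and insomnia are both listed terms. In the week after each session, when such events are most to be expected, 8.2 as written keeps them off the AE page however severe they are and whether or not they are treated. Staff who follow 8.5 could record the same event as an AE. The table the SAP treats as the primary safety measure would then depend partly on which section was followed. The severity of what stayed on the reaction page would be collected but not tabulated under the SAP.

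**Working it through.** The plan gives no figure on this point, so the check is a side-by-side reading with two small counts.

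1. **Size of the list.** Counting the terms in 8.2 gives 27. At least five are psychiatric: Anxiety, Low Mood, Increased Irritability, Insomnia and Rumination. The other terms number 27 − 5 = 22.

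2. **Exits from the reaction page.** Section 8.2 gives one, duration beyond seven days. It gives none for a severe grade, rescue medication, medical attention, withdrawal or change in psychiatric status.

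3. **Where 8.2 and 8.5 agree.** Both contain the seven-day transfer. For a listed reaction that meets no other 8.5 criterion there is no conflict.

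4. **Where they overlap without a precedence rule.** Take severe anxiety that starts on day 2 after a session, is treated with a rescue medication and has gone by day 5.
   - Under 8.2: a listed term lasting less than seven days, so reaction page only.
   - Under the 8.5 bullet on medical attention, which speaks of events and not of AEs: collected, with no exception for listed terms, if the treatment counts as medical attention.
   - Under the 8.5 psychiatric-status bullet: collected if the episode is an AE. The definition in 8.1 covers any symptom temporally associated with participation, related or not, so it can be read to include this one.

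   Two people following the protocol could record this event differently.

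5. **What the choice of page determines.**
   - Severity: the 8.1 definitions, based on limitation of daily activity, apply to the AE CRF.
   - Relatedness: specified for AEs only.
   - Physician review and confirmation under 8.5: AEs and SAEs.
   - SAP severity summary: AEs. The SAP calls reactions commonly reported AEs but gives them their own frequency table, and does not say whether they also enter the AE incidence table.

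6. **Protocol against SAP.** Section 12.0 promises maximum severity and duration for reactions. The SAP safety section plans frequencies. This gap exists whichever way step 4 is resolved.

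7. **Sensitivity of the tables.** Ten dyads are 20 people, so one participant is 1/20 = 5 percentage points of any overall incidence. Within the PTSD+ or the CSO group one participant is 1/10 = 10 points.

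**The case against.** A separate, prespecified page for expected reactions is a legitimate and disclosed choice. The 8.5 bullets can be read as setting how long each kind of AE is collected, not which page is used. The Time and Events table supports this: the row for all AEs stops at Visit 16, while the row for SAEs and for psychiatric and withdrawal AEs runs to Visit 18. On that reading the only firm overlap is a listed reaction needing medical attention. The data are also not lost: reactions are graded and followed to resolution, rescue medication is captured, and the SAP describes itself as based on the protocol's analysis plan, so its silence on severity does not cancel section 12.0.

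Much of this stands. It shows that 8.2 and 8.5 do not contradict each other in general. It does not supply a precedence rule, a relatedness rating for reactions, or the missing SAP tables.

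Two stronger readings are tempting, and the documents do not support them.

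- A reader might infer that acute psychiatric harm is removed from the primary safety measure. It is not. All SAEs are collected. Clinically significant treatment-emergent suicidality is an AE under 7.2.1. Panic and psychosis are not listed terms, so 8.2 itself sends them to the AE page. The SAP tabulates reactions within its safety section, alongside the C-SSRS, distress ratings and General Wellbeing.
- A reader might turn the statement in 7.2 that "anxiety, headache, fatigue, insomnia and lack of appetite were spontaneously reported by 40% to 80% of participants" into an expected number of hidden events here. That range covers both conditions of the earlier trial, spans five terms and says nothing about severity. It also comes from a PTSD trial, whereas half of these participants are CSOs without current PTSD. It cannot size the number of severe or treated reactions left off the AE page.

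**Conclusion.** The point holds in a bounded form. Followed as written, 8.2 leaves a severe or medically treated listed reaction that resolves within seven days off the AE page, and so potentially out of the AE incidence, severity and relatedness tables. Section 8.5 can be read to require the opposite for some of the same events. Separately, the SAP omits the severity and duration tables for reactions that protocol section 12.0 promises.

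The conflict is confined to listed terms that also meet another 8.5 criterion. The number of events concerned cannot be estimated from the documents. The conclusion assumes that the reaction page and the AE page feed separate tables; the SAP layout implies this but does not state it. If reactions were also counted in the AE incidence table, the incidence problem would go, but the missing relatedness rating and the absent severity and duration tables would remain. With safety part of the study's overall objective and only 20 participants, this should be corrected, though it does not undermine the safety evaluation as a whole.

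**What to change.** These changes concern recording and reporting only.

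1. **Protocol 8.2 and 8.5.** Add to 8.2: *A listed reaction that is graded severe, is treated with rescue medication, requires medical attention or leads to withdrawal is also recorded on the AE page from its onset, and is rated for severity and relatedness by the study physician.* State in 8.5 how the psychiatric-status bullet applies to listed terms. I would not use any change in psychiatric status as a trigger without defining it: it could catch nearly every report of low mood or anxiety and merge the two streams.

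2. **SAP, 6. Safety Analyses.** Tabulate reactions by maximum severity and duration, overall and for PTSD+ and CSO participants, as protocol section 12.0 states.

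3. **SAP, same section.** Add one incidence table combining AEs and reactions by preferred term, each participant counted once per term, so that dual recording does not inflate it.

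The cost is some wording in both documents, a few more AE pages and the extra tables. AE counts will look somewhat less favourable. The separate reaction table is kept.
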